A second cost utility analysis will also be performed. This model will also take an NHS perspective and use costs based on HES data as for the cost effectiveness model, but additionally will use outcomes based on QALY data (primary EQ5D data collected through the field work in a subgroup of SIHHC users at baseline and three month follow up). Data from the two types of service will also be compared to each other and homeless controls from a wider London based survey of 455 homeless individuals accessing Find and Treat screening service for tuberculosis. QALY loss due to morbidity and mortality averted will be examined. Cost estimates will be based on HES data and calculated at two time points: baseline, including retrospective data up to 3 month prior enrolment in the study, and follow up, including prospective data up to 3 month service follow up. Outcome data (QALY) will be calculated from EQ5D data collected at baseline and 3 month follow up.

Cost and effectiveness estimates to be calculated for one year follow up period after entering the study with simulations to 20 years and costs will be discounted at 3.5% per annum. A sensitivity analysis will be carried out in order to examine uncertainties within the cost effectiveness and utility model to examine the uncertainty within the parameters used.

A third cost utility analysis will also be performed using costs and health outcome (consented) data collected from the 6 case study sites. This model will take an NHS and also a wider public sector perspective (e.g. exploring costs for use of social care, prison, supported housing etc.).

The added value of this third economic analysis would be to estimate the cost utility of hospital discharge services from a larger public sector perspective whilst incorporating contextual information from the realist evaluation into the economic evaluation.

The objective of this economic evaluation will be to:

- Evaluate the effect of SIHHC on access to resources and their attached costs (health and mental health services, drug and alcohol services, social care services, housing situation) and on individual wellbeing, and how effect may vary across schemes in different sites
- Compare the effect of SIHHC on access to resources and individual wellbeing to sites relying on standard provision only (i.e. those that do not have access to SIHHC)
- Evaluate any variation in effect of SIHHC across time (dependent on opportunities for tracking participants over the longer term)

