Where feasible, data on access to resources will be collected up to 12-month from discharge. This will allow capturing changes in yearly estimate before and after participating in SIHHC. To determine the effect of the SIHHC we will compare individual service use and health outcome after joining the study (based on 3-month follow-up) with our estimate of their service use had they not participated (one year prior to the enrolment). The specialist schemes will then be compared to the standard schemes which will be assessed in the same way. Cost of care will be estimated multiplying individual-specific health care resource utilization by unit cost using available tariff.

Sample size for economic evaluation:

Data from our 455 controls from Find & Treat provides a mean EQ5D visual analogue scale score of 65 and standard deviation of 25. An important improvement (or worsening) in the EQ5D visual analogue scale (0 to 100) as result of the provision of specialist services to this group would be 10. Using a power of 80% at the 0.05 level of significance (two sided) and a two sample *t* means test it is estimated that a sample size of 100 is required to detect such a change. Based on our previous work it is assumed that of all eligible service users identified, 80% of these will consent to take part in the study, and therefore 126 individuals will need to be approached to achieve this sample size. Therefore, 63 individuals will be approached at each of sites 1-6 (for a total of 378 individuals).

Sensitivity analysis and economic discounting: Cost and effectiveness estimates to be calculated for one year follow up period after entering the study with simulations to 20 years and costs will be discounted at 3.5% per annum. A sensitivity analysis will be carried out in order to examine uncertainties within the cost effectiveness and utility model to examine the uncertainty within the parameters used.

Additional ethical issues

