Inclusion Criteria: Service users will be recruited on a first come first served basis until the following demographic categories are filled:

Young Homeless People (1 male/ 1 female) (Age 18-24)

Men in the middle age range (4 male) (Age 25-49) [Known to have the most complex needs (McDonagh, 2011)]

Women in the middle age range (25-49)(2 Female)

Older Homelessness (50+) (1 male/1 female)

NB: Once these categories are filled, homeless service users will then be allocated to **Group B (n=53 service users)**

Group A

Data is to be collected for both Work Package 1 (Realist Evaluation) and Work Package 2 (Comparative Effectiveness and Economic Evaluation)

Homeless service user is on the hospital ward.

Step 1

Seek the support of hospital/scheme discharge coordinators to recruit 10 service users for Group A (n=60)

Step 2

The hospital/scheme discharge coordinator informs the service user about the study, provides an invite letter and a 'Service user Information Leaflet' (Form A). These will be talked through and permission sought to pass the service user's contact details to the research team.

Step 3

A few days after discharge from hospital, the researcher makes contact with the service user (where permission to contact has been given) to arrange a community visit. This will be made by the University Researcher and Peer Researcher working in pairs.

The researcher provides another copy of the 'Service user information Leaflet' (Form A), answers any questions and if the service user is willing to participate

takes informed consent (either written or verbal)(Form A).

Step 4

A semi-structured interview is carried out (Topic Guide 1 – Time 1)

A baseline questionnaire is completed (WP2/BL)

Step 5

Qualitative interview data is transcribed and stored in pass word protected computer at King's College London

Secure upload of consented (WP2BL) individual data to Farr data safe haven

Step 6

The Peer Researcher maintains telephone contact until Time 2 interview takes place at 3 month follow-up (Topic Guide 1 –Interim Telephone)

Notes are taken and passed to King's College London to be stored on pass word protected computer

Step 7

At 3 month follow-up, a semi-structured interview is carried out (Topic Guide 1 – Time 2)

A follow-up questionnaire is completed (WP2/FU)
(University and Peer researcher working in pairs)

Step 8

Qualitative interview data is transcribed and stored in pass word protected computer at King's College London

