Secure upload of consented (WP2FU) individual data to Farr data safe haven (WP2/FU)

Group B

Data is to be collected for Work Package 2 (Comparative Effectiveness and Economic Evaluation) Only

Homeless service user is on the hospital ward.

Step 1

Seek the support of hospital/scheme discharge coordinators to recruit 53 service users for Group B at each site (n=318)

Step 2

The hospital/scheme discharge coordinator informs the service user about the study, provides an invite letter and a 'Service user Information Leaflet' (Form B). These will be talked through and permission sought to pass the service user's contact details to the research team.

Step 3

A few days after discharge from hospital, the researcher makes contact with the service user to arrange a community visit.

The researcher provides another copy of the 'Service user Information Leaflet' (Form B) answers any questions and if the service user is willing to participate takes informed consent (either written or verbal) (Form B)

Step 4

A baseline questionnaire is completed (WP2/BL)

Step 5

Secure upload of consented (WP2/BL) individual data to Farr data safe haven

Step 6

A follow-up questionnaire is completed on exist from the scheme and at three months follow up (WP2/FU)

Step 7

Secure upload of consented (WP2/FU) individual data to Farr data safe haven (WP2)

Box 3: Arrangements for Data Collection in Fieldwork Sites 7-20*

Scheme Typologies Across Sites 7-20

Sites 7-13: In these sites the hospital has access to a specialist integrated hospital discharge scheme for homeless people which is 'clinically-led'

Sites:14-20 In these sites the hospital has access to a specialist integrated discharge scheme for homeless people which is non-clinical (e.g. provides access to housing advice only)

Comparator Databases:

Find and Treat [comparator database]

Hospital Episode Statistics [comparator database representative sample of lowest quintile of deprivation equal in size to the Find and Treat dataset]

Step 1

CAG Approvals in Place

Step 2

Unique study ID created for each individual record and left on site

Step 3

Secure upload of operational service data (non-consented) to Farr data safe haven

[figure not shown]
Step 4

Transfer of sensitive data (first name, surname, dob, sex, current or previous postcodes, nationality, ethnicity, NHS Number, Hospital of admission, Study ID

Step 5:

Transfer of HES ID and HES data back to Farr data safe haven

Box 4: Detailed Data Flow for WP2:

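### The pre-enrolment cost windows contain the index hospital stay, so the third economic analysis uses partly treated time as its no-service counterfactual and gives index-stay effects the wrong sign

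*Protocol*

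**What the plan says.** The Protocol's Health Economics Analysis section describes three models. The primary one is a cost-effectiveness model on readmission outcomes.

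The second is a cost-utility analysis with HES-based costs taken over an earlier and a later period. The earlier period is given as "baseline, including retrospective data up to 3 month prior enrolment in the study". The later period is given as "follow up, including prospective data up to 3 month service follow up". It compares the two service types with each other and with 455 homeless people surveyed through Find and Treat.

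The third is a cost-utility analysis on consented data from the six case study sites. It will "compare individual service use and health outcome after joining the study (based on 3-month follow-up" and set this against "our estimate of their service use had they not participated (one year prior to the enrolment". Specialist schemes are then compared with standard sites that are handled the same way.

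Appendix One, Box 2 gives the timing. Recruitment starts from this state: "Homeless service user is on the hospital ward". For Group B (53 of 63 people per site), "A few days after discharge from hospital, the researcher makes contact with the service user to arrange a community visit". At that visit the study worker "answers any questions and if the service user is willing to participate takes informed consent (either written or verbal) (Form B", and the baseline questionnaire follows. Group A (the other 10 per site) runs on the same clock: "A few days after discharge from hospital, the researcher makes contact with the service user (where permission to contact has been given".

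Nothing in the Protocol removes the index stay from the before-period or assigns it to the after-period. The costs defined for the primary model, which the second model reuses, include length of stay and emergency admissions.

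**The concern.** A before-period that stands for use without SIHHC should contain no SIHHC activity and should not be selected on the event that brings people into the study. This one fails on both counts.

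First, everyone is found through a hospital admission. The before-period therefore holds one certain admission per person and the after-period holds none, so use falls within person even if the service does nothing.

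Second, SIHHC works during that admission. The background sections describe ward assessments, ward rounds, case conferences and link workers seeing clients in hospital. Any effect of the service on the index stay is therefore booked as baseline and subtracted. Length of stay is a live question in this study: it is a secondary outcome, and the background cites both an earlier review reporting a 30% reduction in bed days and a worry that such teams might delay discharge.

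The third analysis is the only one with a wider public sector perspective, and its specialist-versus-standard contrast is the question in the study's title. Commissioners could be shown savings at every site that arise from the window definition, and an inpatient component whose sign is reversed between arms.

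**Working it through.** The Protocol states no before-and-after figure to reproduce. Its admission rate comes from the comparative effectiveness sample size, which does reproduce: (0.84 + 1.96)² × (0.7 + 0.6) / (0.7 − 0.6)² = 1,019 person-years per group.

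**Inputs**
- Rate r = 0.7 admissions per person-year (Sample size section), taken as constant, with no service effect.
- Before-window W: 12 months (third analysis) or 3 months (second), ending at enrolment.
- After-window: 3 months in both.
- Enrolment: the consent visit a few days after discharge (Appendix One, Box 2).
- Index stay L: not given. Assumed range 3 to 28 days.

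**Formulas**
- Expected admissions before = 1 + r × (W − L)/365, with W and L in days.
- Expected admissions after = r × length of the after-window in years. Over 3 months this is 0.7 × 0.25 = 0.175; annualised it is 0.7.

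**Third analysis, 12-month before-window**
- Ignoring L: before = 1 + 0.7 = 1.7.
- L = 3: before = 1 + 0.7 × 362/365 = 1.694. L = 28: 1 + 0.7 × 337/365 = 1.646.
- After, annualised: 0.7. Fall = 1 − 0.7/1.694 = 59% and 1 − 0.7/1.646 = 57%.
- After, raw 3-month count: 0.175. Fall = 90% and 89%.
- At four times the rate (2.8 per year), annualised: 3.777 to 2.8 (26%) for L = 3, and 3.585 to 2.8 (22%) for L = 28.

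**Second analysis, 3-month before-window**
- Ignoring L: before = 1 + 0.175 = 1.175; after = 0.175, an 85% difference.
- L = 3 to 28: before = 1.169 to 1.121, a difference of 85% to 84%.

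**Contrast with standard sites**
- Let the index stay cost s under standard care and s + c under SIHHC, with the same background cost b on each side of the index stay.
- As written: [b − (s + c + b)] − [b − (s + b)] = −c.
- With the index stay costed in the after-period: [(s + c + b) − b] − [(s + b) − b] = +c.
- Illustration with an assumed 7-day standard stay and SIHHC stays 2 days longer: as written −9 − (−7) = −2 bed-days, an apparent saving; with the stay in the episode 9 − 7 = +2 bed-days.

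**Check of the remedy**
If the before-window ends at index admission, expected background counts match with no effect: 0.175 against 0.175 over 3 months, and 0.7 against 0.7 over a year.

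**The case against.** Several counter-arguments have weight.

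- **The second analysis states no subtraction.** Its text gives two costing time points and the groups to be compared. Only the third analysis calls prior use the estimate of use without the service. This stands: a reader might infer that the second analysis also takes its baseline as the counterfactual, but the Protocol does not say so, and how the two points are combined may be left to an analysis plan. What remains there is narrower: the baseline cost contains an index stay, while Find and Treat controls were not selected through an admission.
- **The third analysis may annualise.** The same paragraph speaks of yearly estimates, with data to 12 months where feasible. A reader might therefore take the 90% figure as the built-in fall, but it applies only if a raw 3-month count is set against 12 months.
- **The control sites absorb the artefact.** They cancel the common part if index stays cost the same in both groups. They do not cancel a difference caused by SIHHC.
- **That difference may be small.** The trial summarised in the background found no change in length of stay. That is fair, but it tested one model (Pathway), and the present study covers several, including schemes without clinical input.
- **Enrolment is not defined.** The linked cohort enters at first admission, and the section on data sets says discharge projects may help collect questionnaires, so some baselines could be taken on the ward. For fieldwork participants the consent visit is the natural reading. Even with ward enrolment, the admission and part of the stay would precede it.

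**Conclusion.** The concern holds for the third analysis. As described, its before-period contains the index stay. With no service effect this produces a within-person fall in expected inpatient admissions from about 1.7 to 0.7 per year (57–59% annualised). An SIHHC effect of c on index-stay cost is reported as −c, an error of 2c per person; the documents do not allow c to be sized. These results assume enrolment at the post-discharge consent visit, a constant rate of 0.7 per year and index stays of 3–28 days.

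For the second analysis, the conclusion is limited to a baseline cost that contains the index stay and does not match its Find and Treat controls.

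Two stronger inferences should be resisted. The percentages count admissions, so they do not show an equal fall in total cost, especially as the third analysis also covers social care, prison and supported housing. Nor is the whole economic evaluation undermined: the primary cost-effectiveness model rests on readmission outcomes and is not shown to use either window. This should be fixed, but as a fault in secondary economic analyses.

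**What to change.** In the descriptions of the second and third analyses:

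1. End the before-period on the day before the index admission.
2. Cost the index stay, from admission, as part of the intervention episode, identically in specialist, standard and any other admission-based group. State how the Find and Treat group, which has no index stay, is to be compared.
3. Put before and after on the same time scale, by equal windows or explicit annualising.

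The change-from-baseline comparison with standard sites can stay; replacing it with an adjusted comparison of after-period cost is a matter of preference and is not needed.

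The cost is modest. Admission and discharge dates and all previous admissions are already requested from HES, so that part is recoding. Box 5 lists hospital-use and accommodation items over the last year; wherever the questionnaires use that recall period, they need a reference date before the index admission. Equal 12-month windows would depend on follow-up promised only where feasible, so explicit annualising may be the practical choice. The within-site savings will look less favourable.

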1. **Unconsented data:** SIHHC (hospital discharge projects) taking part in the study (Sites 1-2, 7-13 using clinically led services; Sites 3-4, 14-20 using non-clinically led services) will be asked to provide identifying and demographic data (forename, surname, aliases, date of birth, sex, current or previous postcodes, nationality, ethnicity, NHS number) for service users during the period November 2013 to a maximum of November 2016. However, note that for some services we will collect data that ends before 2016 as some will have been shut down before this time period and in some we may collect data at an earlier point, providing we receive the appropriate permissions and ethical and CAG approvals.
2. **Consented data from a subset of study fieldwork sites (n=6 sites):** We will collect data on 252 individuals across 4 sites with SIHHC (hospital discharge) schemes (two sites that are clinically led (Sites 1&2), two sites that are non-clinically led (Sites 3&4)) and on 126 individuals across two sites with standard /usual care (Sites 5&6), giving 378 individuals in total (63 per site x 6 sites). The data collection for this part of the work is contained in a baseline, exit and 3-month follow up data questionnaire and will collect information on demographic information, along with dates of contact with SIHHC services, past use of health and social care services, mental health services, smoking, alcohol, and drug taking history, prison and homeless history, employment, user satisfaction with service delivery, and data on quality of life (EQ5D). The voluntary sector hospital discharge projects will be asked to help collect this data on behalf of the research team as part of their routine outcomes monitoring and will be reimbursed for doing so at a rate of £20 per completion. The data flow chart shows how this work will be integrated with WP1 for practical purposes.
3. The data flow chart shows how this work will be integrated with WP1 for practical purposes.

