We will provide data from the 20 sites and Find and Treat to the Health & Social Care Information Centre (HSCIC). These records will be list cleaned and then linked by HSCIC to the Hospital Episode Statistics (HES) database to provide data on hospitalisations and A&E attendances and deaths for individuals in the 20 sites and Find and Treat database. In order to be able to identify co-morbidities more accurately we will request data on all previous admissions for these groups for identification of

comorbidities but analyses of admission rates will be confined to the period November 2008 – November 2016.

Study design:

We will construct a virtual cohort that will take first date of admission as the entry point (earliest November 2008) or, for control groups an admission matched by month and year restricted to individuals over the age of 18. Exit from the virtual cohort will be at the end of November 2016 or, if earlier, date of death. We will conduct person-level analyses using Poisson regression to compare overall hospitalisation rates, emergency admission rates, all cause mortality and avoidable mortality rates in:

- 1) Homeless people using the different categories of SIHCC service (clinically led services - sites 1&2, 7-13; non-clinically led services - sites 3&4, 14-20)
- 2) Find and Treat Homeless population and sites 5&6 with standard usual care
- 3) Socially deprived non-homeless population.

We will also conduct analyses at the level of the hospital admission whereby through knowledge of the dates of SIHCC involvement and service user group we will be able to classify hospital admissions in the period November 2008- November 2016) into the following groups:

- 1) Admissions in a socially deprived non homeless population
- 2) Admissions in the general homeless population (Find and Treat data)
- 3) Admissions in homeless service users prior to their first engagement with SIHCC
- 4) Admissions in homeless service users where there is evidence of SIHCC support for that admission
- 5) Admissions in homeless service users that occur following SIHCC support but where there is no record of support for the subsequent admission.

We will use Cox regression survival models and Kaplan Meir plots (accounting for clustering at the level of the hospital and individual) to explore how admissions in these groups compare in terms of the following primary outcomes:

- 1) Time from discharge to next A&E attendance

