μ_1 = mean readmission rate in the SIHHC group = 0.6 episodes per person-year

$v=1.96$ =percentage point of the normal distribution corresponding to a 5% two-sided significance level

$u=0.84$ =one-sided percentage point of the normal distribution corresponding to (100%- type II error [FN / (TP + FN)]) at 80% power

Using the following equation we estimated minimum sample size (per group) required for comparison of two rates (readmissions per person-year):

$$\begin{aligned} & (u+v)^2 * (\mu_1 + \mu_0) / (\mu_1 - \mu_0)^2 \\ & (0.84+1.96)^2 *(0.7 + 0.6) / (0.7 - 0.6)^2 \\ & =1019 \text{ person-years per group} \end{aligned}$$

Adjustment for confounders as far as is possible within the analysis results in a doubling of sample size (additional 10% per confounder; likely 10 confounding variables). Therefore 2038 person-years are required per group. Assuming that the SIHHC clinically led and non-clinically led sites see on average 90 service users each month during the study period (which for the purposes of this calculation we have assumed this to be November 2013-November 2015 as many services may have been shut down before this time period and in some we may collect data at an earlier point) we estimate that this translates to a total 2,160 individuals at each of these two types of service.

Follow up: For the primary analysis, individuals will enter the cohort on date of first hospital admission (earliest November 2008) and will be censored at the end of the study period (November 2016) or death, whichever ever comes first.

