Confounding variables: As this is a virtual cohort, we will not be able to collect a complete set of confounding variable data on individuals at entry to the study. Where data is provided by SIHHC services we will include age (year and month only), sex. As a result of the lack of baseline data will use historical HES data to determine past medical history from the age of 18 which will be used to create a variable to control for co-morbid conditions and historical hospital usage. Analyses will therefore control for age, gender, comorbidities (identified from HES data) and reason for admission, classified by Healthcare Resource Group (HRGs – groupings of treatment episodes which are similar in resource use and clinical response). Subgroup analyses will compare the different types of SIHCC services. Where provided by the SIHHC services, we will also control in subgroup analysis for medical symptoms, past use of health and social care services, mental health services, smoking, alcohol, and drug taking history, prison and homeless history, employment history.

Health Economics Analysis:

This analysis will cover three economic models. The primary analysis will be a cost effectiveness model (linked to effectiveness data described in the comparative effectiveness section). This model will take an NHS perspective, with costs based on the linked HES data analysis and outcomes based on morbidity and mortality data. Outcomes of homeless users of the two types of SIHHC service (clinically led and non-clinically led) will be compared to each other and homeless controls. Outcomes used for this analysis will include: 1. Overall hospital readmission rates; 2. Unscheduled readmission rates; 3. 28-day emergency readmission rates. Cost estimates will be calculated using national NHS

tariff data, and will include length of hospital stay, emergency admissions, and fixed and variable costs estimates for each of the SIHHC services.

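### The one-year horizon of the HES-based economic estimates does not fit the data window: scheme users may be taken up to November 2016, the month in which linked follow-up ends

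*Protocol*

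**What the plan says.** Horizon. Health Economics Analysis: "Cost and effectiveness estimates to be calculated for one year follow up period after entering the study with simulations to 20 years". The later paragraph on sensitivity analysis and discounting repeats this. The primary model takes its costs from linked HES data, and "Outcomes of homeless users of the two types of SIHHC service (clinically led and non-clinically led) will be compared to each other and homeless controls".

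Intake. Data sets used for WP2, item 1, asks the schemes for data "for service users during the period November 2013 to a maximum of November 2016". It adds that "for some services we will collect data that ends before 2016 as some will have been shut down before this time period".

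End of follow-up. Study design: "Exit from the virtual cohort will be at the end of November 2016 or, if earlier, date of death".

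Entry. The Follow up paragraph after the sample size says that "individuals will enter the cohort on date of first hospital admission (earliest November 2008) and will be censored at the end of the study period". Study design gives controls an admission matched by month and year.

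Sample size. Of the study period, this section says: "which for the purposes of this calculation we have assumed this to be November 2013-November 2015 as many services may have been shut down".

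Second economic model. Health Economics Analysis describes its HES costs as covering up to 3 months before enrolment and up to 3 months after, shortly before giving the one-year horizon.

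**The concern.** The latest permitted intake date is also the data cut-off, yet the economic estimates need a year after entry. The protocol does not limit the one-year estimates to people who can be followed for a year. It also does not say which event starts the economic year.

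On one reading of entry the year is truncated for late users. On the other it may be a year in which the person had not yet met a scheme. Either way the cost side of the primary economic model is affected. Scheme costs arise around contact and are counted whole, while the hospital use that should offset them is cut short. The 20-year simulations start from the same one-year values.

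**Working it through.** **Plan's own figures.** (0.84 + 1.96)² × (0.7 + 0.6) / (0.7 − 0.6)² = 7.84 × 1.3 / 0.01 = 1,019 person-years per group. Doubled for confounders this is 2,038. Intake is 90 × 24 months = 2,160 per service type. All three reproduce. The 24 months are November 2013 to November 2015, so in that calculation everyone has at least a year before the cut-off.

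**Reading A: the year starts at scheme contact.** Inputs: intake from November 2013 to at most November 2016 (36 months), cut-off at month 36, horizon 12 months. Assumption: even intake in the first 24 months, with the last 12 months at a fraction r of that rate. Users entering in the last 12 months have 6 months on average.

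- Share without a full year = 12r / (24 + 12r)
- Part of first-year time observed = (24 × 12 + 12r × 6) / ((24 + 12r) × 12)

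| r | Share short of a year | First-year time observed | Unobserved |
|---|---|---|---|
| 1 | 12/36 = 33.3% | 360/432 = 0.833 | 16.7% |
| 0.75 | 9/33 = 27.3% | 342/396 = 0.864 | 13.6% |
| 0.5 | 6/30 = 20.0% | 324/360 = 0.900 | 10.0% |
| 0.25 | 3/27 = 11.1% | 306/324 = 0.944 | 5.6% |
| 0 | 0% | 1.000 | 0% |

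At 90 per month, r = 1 means 1,080 of 3,240 users per type. Intake before November 2013, which item 1 allows for some services, would lower these shares.

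**Effect on summed costs.** If cost accrues evenly over the year and observed costs are simply added up, the understatement equals the last column, at most 16.7%. If the rate is assumed to be 2 or 3 times higher in the first 3 months, the understatement at r = 1 falls to about 14% or 12.5%. Dividing by person-time would instead overstate by about 3% or 5%. The documents give no figure for such early clustering.

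**Effect on readmissions.** A raw count at a true rate of 0.7 would read 0.7 × 0.833 = 0.58 per person. A rate per person-year stays at 0.7 if the rate is constant. With even intake over 36 months, only about 2.6% of entrants lack 28 days of follow-up.

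**Reading B: the year starts at first admission since November 2008.** A person first admitted before November 2012 has a one-year window that closes before scheme intake begins in November 2013. The share affected cannot be computed, because the documents do not give the distribution of first admissions. Fewer people are truncated on this reading, but for some the year costed is a year without the scheme.

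**The case against.** The strongest reply is that the effectiveness analyses already allow for unequal follow-up: "We will conduct person-level analyses using Poisson regression to compare overall hospitalisation rates, emergency admission rates". Cox models are planned for the times to event, individuals are censored, and the primary economic outcomes are readmission rates linked to those analyses. This stands for the readmission outcomes. It does not reach costs, for which the protocol gives tariff-based totals and neither states nor excludes an allowance for censoring.

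A second reply is that a method for censored costs belongs in an analysis plan that may exist. That is fair for the choice of estimator. The dates and the entry rule, however, are fixed in the protocol, and no later plan can supply follow-up beyond the data window.

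A third is that November 2016 is a ceiling and that many services may have closed earlier. This is why the share is a range starting at 0%.

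A reader might infer that services running to November 2016 would look better than those that closed early, by about as much as the effect the study is sized for (0.1/0.7 = 14.3%). The documents do not support this. They give no closure dates by service type and assume the same monthly intake for both. A 16.7% gap between types would need raw totals, with every service of one type running to the end and every service of the other stopping by November 2015. A reader might also suppose that controls enter earlier and so look worse, but control admissions are to be matched by month and year, which balances the cut-off.

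**Conclusion.** The conflict of dates holds. Following the protocol as written gives either a truncated year (scheme contact as time zero) or, for some people, a year before exposure (first admission as time zero).

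On the first reading 0% to 33% of scheme users lack a full year. The upper end assumes even intake to November 2016; a larger share would need intake to rise in the last year, which nothing in the protocol suggests. One-year hospital costs would be understated by up to 16.7% only if they are summed without allowing for censoring and accrue evenly over the year. Bias in the readmission rates, or between the two service types, is not established. The point merits a correction to the economic section and does not call the effectiveness analyses into question.

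**What to change.** In Health Economics Analysis and in Sensitivity analysis and economic discounting:

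1. Define the economic time zero as the index scheme-supported admission, and for controls as the admission matched by month and year.
2. Limit the one-year cost and effectiveness estimates to index admissions ending on or before 30 November 2015, so that everyone has 12 months of potential HES/ONS follow-up. Keep people who die as observed, with no cost after death.
3. Add a sensitivity analysis of all entrants to November 2016 with a censoring-adjusted cost estimator (partitioned or inverse-probability-weighted by month since entry).
4. Reconcile the one-year horizon with the 3-month cost windows stated for the second model.

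Later entrants stay in the Poisson and Cox analyses.

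The cost is a few sentences and a date filter, plus an economic index event that differs from the cohort entry rule and must be stated as such. Up to a third of scheme users would be left out of the main one-year estimates. The stated 2,160 per type is unaffected, because it already assumes intake only to November 2015.
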